1.3.2 Potential Risks to Subjects

Like other vaccines, MenACYW conjugate vaccine may cause injection site reactions such as pain, swelling, and erythema, or certain systemic events such as fever, headache, malaise, and myalgia. There may be a rare possibility of an allergic reaction, which could be severe. There may also be a risk of febrile convulsion in some children who experience high fever. There may be other risks for MenACYW conjugate vaccine that are not yet known.

been reported following the administration of MenACYW conjugate vaccine in any other trials.

Guillain-Barré syndrome (GBS) has been reported mostly in persons aged 11 to 19 years who had symptom onset within 6 weeks of administration of a US licensed meningococcal conjugate vaccine (29). A retrospective cohort study carried out in the US using healthcare claims data found no evidence of increased GBS risk associated with the use of that vaccine. The study was able to exclude all but relatively small incremental risks (30).

A review by the Institute of Medicine (IOM) found inadequate evidence to accept or reject a causal relationship between tetanus toxoid containing vaccines and GBS (31). The IOM found evidence for a causal relation between tetanus toxoid-containing vaccines and brachial neuritis (32). Arthus reactions are rarely reported after vaccination and can occur after tetanus toxoid-containing vaccines (33).

No occurrences of GBS, brachial neuritis, or Arthus reaction have been reported with the use of MenACYW conjugate vaccine in the completed clinical trials.

The risk of vasovagal syncope exists after any vaccination in the adolescent age group, although it has not been specifically reported in the age group under study as part of this protocol (34). A few cases of immediate vasovagal-like response or syncope have been observed in adolescent subjects who had received MenACYW conjugate vaccine.

The potential risks associated with blood drawing include local pain, bruising, and, rarely, fainting. Infection at the site of needle insertion could theoretically occur but is exceedingly rare when the standard sterile technique is utilized.

The potential risk listed here are not exhaustive. Refer to the Investigator's Brochure of the investigational vaccine for additional information regarding the potential risks.

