9.2.3.4 Adverse Events of Special Interest

9.2.3.5 Assessment of Causality

The Investigator will assess the *causal relationship* between each unsolicited systemic AE and the product administered as either *not related*, based on the following definitions:

Not related – The AE is clearly / most probably caused by other etiologies such as an underlying condition, therapeutic intervention, or concomitant therapy; or the delay between vaccination and the onset of the AE is incompatible with a causal relationship; or the AE started before the vaccination (screening phase, if applicable)

Related – There is a "reasonable possibility" that the AE was caused by the product administered, meaning that there is evidence or arguments to suggest a causal relationship

Note: By convention, all AEs reported at the injection site (whether solicited or unsolicited) and all solicited systemic AEs are considered to be related to the administered product and therefore are referred to as reactions and do not require the Investigator's opinion on relatedness.

Adverse events likely to be related to the product, whether serious or not, that persist at the end of the study will be followed up by the Investigator until their complete disappearance or the stabilization of the subject's condition. The Investigator will inform the Sponsor of the date of final disappearance of the event or the date of "chronicity" establishment.

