**Table 3.1: Study procedures** 

Phase III Study, 2 Visits, 1 Vaccination, 2 Blood Samples, 1 Telephone Call, 30 Days Duration per Subject

Visit/Contact	Visit 1	Telephone Call 1	Visit 2
Trial timelines (days)	D0	D08	D30
Time windows (days)		+2 days	+14 days
Informed consent	X		
Inclusion/exclusion criteria	X		
Collection of demographic data	X		
Medical history	X		
Physical examination*	X		
Review of temporary contraindications for blood sampling †			X
Allocation of subject number	X		
Blood sampling (BL), 5 mL ‡	BL1		BL2
Vaccination §	X		
Immediate surveillance (30 minutes)	X		
Diary card (booklet or e-diary) provided	X		
Telephone call		X**	
Recording of solicited injection site & systemic reactions	D0 to D07		
Recording of unsolicited AEs	D0 to Visit 2		•
Reporting of SAEs (including AESIs) ††	To be reported throughout the study period		study period
Diary card (booklet or e-diary) reviewed and collected			X
Collection of reportable concomitant medications	X		X
Trial termination record			X

\*Temperature needs to be measured and recorded in source documents.

† Should a subject receive oral or injectable antibiotic therapy within 3 days prior to the second blood draw, the Investigator will postpone that blood draw until it has been 3 days since the subject last received oral or injectable antibiotic therapy. Postponement must still be within the timeframe for blood draw (30 to 44 days after vaccination at D0). If postponement would result in the sample collection falling outside of the 30 to 44 day timeframe, the blood sample should be collected without postponement and it should be documented that the sample was taken less than 3 days after stopping antibiotic treatment.

<sup>‡ Blood sample at Visit 1 will be drawn before administration of vaccine

§ Subjects will receive 1 dose of MenACYW conjugate vaccine

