#### **4.4.1.2.4** Time of Onset

Time of onset is derived from the start date of the unsolicited non-serious AE provided in the clinical database and the date of last vaccination:

• start date of the unsolicited non-serious AE – date of previous vaccination

The time of onset should be considered as missing only if one or both of the dates are missing or partially missing.

The unsolicited non-serious AEs will be analyzed "Within 30 days", which corresponds to AEs with a time of onset between D0 and D30 days after vaccination or missing. An AE with missing time of onset will be considered to have occurred just after the vaccination indicated by the visit number, so will be included in these tables.

Note: Unsolicited non-serious AE that occurred before vaccination (negative time of onset) or with a time of onset higher than defined above will not be included in analysis, but will be listed separately.

Time of onset will be displayed as follows:

- D0-D3
- D4-D7
- D8-D14
- $\geq$  D15
- Missing

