#### **4.4.1.3.2** Time of Onset

Time of onset will be computed using the same methodology as for unsolicited non-serious AEs described in Section 4.4.1.2.4.

SAEs will be analyzed throughout the study using the following periods:

- Within 30 days
- During the study (i.e., all SAEs that occurred during the study)

An SAE with missing time of onset will be considered to have occurred just after the vaccination indicated by the visit number, so will be included in these tables.

Note: SAEs that occurred before vaccination (negative time of onset) will not be included in analysis, but will be listed separately.

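### Unsolicited AEs with a partial start date are counted within 30 days even when the known month lies wholly outside D0–D30, and SAP 5.3.1.5 adds a conflicting stop-date rule.

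*SAP*

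**What the plan says.** SAP 4.4.1.2.4 derives onset for a non-serious unsolicited AE as "start date of the unsolicited non-serious AE – date of previous vaccination". It then says "The time of onset should be considered as missing only if one or both of the dates are missing or partially missing", the two dates being the start date and the vaccination date. Onset from D0 to D30, or missing, counts as within 30 days. The reason given is that "An AE with missing time of onset will be considered to have occurred just after the vaccination indicated by the visit number". A note excludes an "Unsolicited non-serious AE that occurred before vaccination (negative time of onset", and likewise an onset beyond D30, and sends both to a separate listing. The onset display has its own Missing row.

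SAP 5.3.1.5 repeats that partial start dates are not imputed and that AEs with missing onset are included according to the visit. It also says that onset is missing if either the start or the stop date is missing or partial. SAP 4.4.1.2.4 does not mention the stop date.

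For SAEs, SAP 4.4.1.3.2 uses the same onset method, reports a 30-day period and a whole-study period, and states that "SAEs that occurred before vaccination (negative time of onset) will not be included in analysis". SAEs with missing onset go into both tables.

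**The concern.** The SAP intends that events known to fall outside D0–D30 are listed, not counted. The rule for partial dates defeats that intention, because it discards the month and year even when they settle the question. Two records of the same event, one with the day and one without, then end up in different outputs, and it is the vaguer record that is counted.

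Both ends of the window are affected. The late end arises in ordinary conduct: unsolicited AEs are collected to Visit 2, which may be as late as D44, so events starting on D31–D44 are properly recorded but are not meant for the 30-day tables.

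The stop-date wording in 5.3.1.5 is a separate defect with the same result. Protocol 9.2.3.3 treats an AE with no stop date as ongoing at study end. Under 5.3.1.5 every such AE would lose its onset day, however complete its start date.

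At stake are the 30-day unsolicited AE percentages, the 30-day SAE table and the onset breakdown. The study tests no hypothesis, so these descriptive figures are themselves the safety result.

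**Working it through.** The plan gives no figure to reproduce here; SAP 5.5 states that no sample size calculation was done. The check applies the written rules to example dates.

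**Inputs.** Onset = start date − vaccination date, in whole days (SAP 4.4.1.2.4). Window D0 to D30 (same section). Visit 2 at D30 + 14 days, so up to D44 (SAP 3.1). Planned N = 188 (Protocol synopsis). The vaccination date of 20 March 2018 is assumed for illustration and lies within the planned inclusion period. It gives D30 = 19 April and D44 = 3 May.

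**Partial start dates, visit number present**

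| Recorded start | Earliest to latest possible onset | SAP as written | With a range check |
|---|---|---|---|
| 19 March 2018 (full) | D−1 | listed | listed |
| February 2018, day missing | D−47 to D−20 | onset missing, counted | listed |
| 2017, day and month missing | latest 31 December = D−79 | onset missing, counted | listed |
| March 2018, day missing | D−19 to D11 | onset missing, counted | counted (ambiguous) |
| April 2018, day missing | D12 to D41 | onset missing, counted | counted (ambiguous) |
| May 2018, day missing | from 1 May = D42 | onset missing, counted | listed |
| 20 April 2018 (full) | D31 | listed | listed |

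Day counts: 1 February to 20 March is 27 + 20 = 47 days, and 28 February to 20 March is 20 days. 31 December to 20 March is 31 + 28 + 20 = 79 days. 20 March to 1 May is 11 + 30 + 1 = 42 days. Three rows (February, 2017, May) are counted although no possible day falls within D0–D30.

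**Complete start date, stop date missing**

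| Start | By 4.4.1.2.4 | By 5.3.1.5, read literally |
|---|---|---|
| 19 March 2018 | D−1, listed | onset missing, counted |
| 24 April 2018 | 11 + 24 = D35, listed | onset missing, counted |
| 25 March 2018 | D5, in the D4–D7 row | onset missing, in the Missing row |

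The two sections give different outputs for all three records. The last row shows that the conflict also alters the onset breakdown for AEs properly inside the window.

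**Scale.** One child wrongly counted: 1/188 = 0.53%. For an AE term with no true case, the exact (Clopper-Pearson) result moves from 0/188 = 0.00% (95% CI 0 to 1.94) to 1/188 = 0.53% (0.01 to 2.93). By priming group, assuming 86 children (the MET54 D30 denominator for Nimenrix in Protocol 1.2.1.2), 0.00% (0 to 4.20) becomes 1/86 = 1.16% (0.03 to 6.31).

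**The case against.** *Counting AEs with unknown onset is a conservative convention.* This stands for dates that are truly ambiguous, such as the March and April rows, and the correction leaves them counted. It does not justify counting an event whose known month already rules out the window, since the SAP itself chooses to list such events.

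*Such records should be rare.* For the pre-vaccination side this largely stands. Collection starts at Visit 1, the diary asks for events after vaccination (Protocol 9.2.3.3), earlier illness belongs in medical history (5.2.6), pre-existing conditions are not AEs unless they worsen (9.2.1), and data are checked and queried before lock (11.2; SAP 5.6). Even so, the SAP foresees pre-vaccination AEs, because it has a rule for them. These safeguards do not address AEs on D31–D44, which are legitimately collected.

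*The events stay visible.* True: they appear in the Missing onset row and do not inflate D0–D3. They do still enter the 30-day total.

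*A stronger reading.* A reader might infer that the SAP also misclassifies Day 0 events caused by the baseline blood draw. The table of procedures notes "Blood sample at Visit 1 will be drawn before administration of vaccine", and Protocol 1.3.2 says "The potential risks associated with blood drawing include local pain, bruising, and, rarely, fainting". A whole-day difference indeed cannot order events within Day 0, so such an event would have onset 0. The documents do not support treating that as an error in the plan:

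- Keeping Day 0 events is a defensible conservative convention, and removing them on site judgement in an open-label study risks under-counting.
- Protocol 9.2.3.5 makes it a ground for a not-related rating if the event began earlier ("or the AE started before the vaccination (screening phase, if applicable"). This affects attribution, not the all-AE count.
- Systemic AEs in the 30 minutes after injection carry an immediate flag, which a faint at the draw should lack. For SAEs, elapsed time and relationship to study procedures are also recorded.
- No rate of draw events recorded as AEs is given, so the size cannot be estimated.
- The SAP describes conduct in the past tense, which suggests that a new CRF item would come too late.

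**Conclusion.** The point holds for partial start dates and for the stop-date conflict. As written, SAP 4.4.1.2.4 and 5.3.1.5 tabulate within 30 days some AEs whose recorded month and year place them wholly before vaccination or wholly after D30, against the SAP's own exclusion. The stop-date clause in 5.3.1.5 contradicts 4.4.1.2.4 and, taken literally, does the same to ongoing AEs with a complete start date.

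The effect is a small over-count: 0.53 percentage points per child in the 30-day totals at N = 188, with the event shown in the Missing row. MET54 randomised 188 subjects and every participant must come from it, so 188 is a ceiling and 0.53 a floor per child for the overall group. How many children would be affected cannot be derived from the documents.

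This rests on a literal reading of the rules and on the AE carrying a visit number. Without one, SAP 4.4.1.2.3 falls back on the start date and does not say what happens if that date is partial. The Day 0 question is at most a limitation to state.

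**What to change.** 1. In SAP 4.4.1.2.4, for a partial start date, compute the earliest and latest possible onset from the known parts. If the whole range is before vaccination or after D30, send the AE to the existing separate listing. Otherwise keep the present inclusive rule and the Missing row.
2. In SAP 4.4.1.3.2, apply the same check to SAEs. If the whole range is before vaccination, list the SAE only. If it is after D30, leave the SAE out of the 30-day table but keep it in the whole-study table.
3. In SAP 5.3.1.5, delete *or stop* from the onset rule, so that onset depends only on the start and vaccination dates. A missing stop date would then affect duration only, as 4.4.1.2.5 already provides.
4. At most, add a sentence to the report that Day 0 events cannot be ordered relative to the injection by date alone.

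The cost is a few sentences in the SAP and a little derivation code. No new data are needed and the CRF does not change.

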#### 4.4.1.2.5 **Duration**

Duration is derived from the start and stop dates of the unsolicited non-serious AE provided in the clinical database:

• stop date of unsolicited non-serious AE - start date of unsolicited non-serious AE + 1.

The duration should be considered as missing only if one or both of the start and stop dates of the unsolicited non-serious AE is missing or partially missing.

Duration will be displayed by period as following:

- 1-3 days
- 4-7 days
- 8-14 days
- $\geq 15 \text{ days}$
- Missing

#### 4.4.1.3 **SAEs**

#### 4.4.1.3.1 Last Vaccination

Last vaccination before an SAE is derived from the visit numbers provided in the clinical database and is calculated as follows:

- If an SAE has a non-missing visit number, the visit number should be used to determine the last vaccination before the SAE
- If the visit number is missing, then the start date should be used to determine the last vaccination before the SAE

#### **4.4.1.3.2** Time of Onset

Time of onset will be computed using the same methodology as for unsolicited non-serious AEs described in Section 4.4.1.2.4.

SAEs will be analyzed throughout the study using the following periods:

- Within 30 days
- During the study (i.e., all SAEs that occurred during the study)

An SAE with missing time of onset will be considered to have occurred just after the vaccination indicated by the visit number, so will be included in these tables.

Note: SAEs that occurred before vaccination (negative time of onset) will not be included in analysis, but will be listed separately.

#### 4.4.1.3.3 **Duration**

Duration will be computed using the same methodology as for unsolicited non-serious AEs described in Section 4.4.1.2.5.

#### 4.4.1.4 Other Safety Endpoints

#### **4.4.1.4.1 Pregnancy**

Not applicable for this study.

#### **4.4.1.4.2 Action Taken**

This information will be summarized as collected, including missing observations. No derivation or imputation will be done.

#### 4.4.1.4.3 Seriousness

This information will be summarized as collected. No derivation or imputation will be done.

#### 4.4.1.4.4 **Outcome**

This information will be summarized as collected. No derivation or imputation will be done.

#### 4.4.1.4.5 Causality

This information will be summarized as collected. An adverse reaction (AR) is defined as an unsolicited non-serious AE or an SAE with causality to the vaccine. Missing causality (relationship) will be handled as described in Section 5.3.1.2.

#### 4.4.1.4.6 AEs Leading to Study Discontinuation

A flag is available in the clinical database for all AEs in order to identify AEs leading to discontinuation.

In general, the items that are counted are:

- Disposition table: A subject who has, on the termination form, the reason for early termination "Serious Adverse Event" or "Other adverse event" is checked
- Safety overview table: A subject who has either on the termination form, the reason for early termination "Serious Adverse Event" or "Other adverse event" is checked or lists an AE on an AE page (solicited, unsolicited, or SAE) that has "Reaction Leading to Termination" or "Event Leading to Termination" or "Serious Adverse Event Leading to Termination" checked that is at least Grade 1 and is within the time period indicated
- SOC/PT table: An event (solicited, unsolicited, or SAE) that has "Reaction Leading to Termination" or "Event Leading to Termination" or "Serious Adverse Event Leading to Termination" checked that is at least Grade 1 and is within the time period indicated

## 4.4.1.4.7 **AEs of Special Interest**

## 4.4.2 Immunogenicity

### 4.4.2.1 Computed Values for Analysis

In order to appropriately manage extreme values (< LLOQ and  $\ge$  ULOQ) for analysis purposes, the following computational rule will be applied to the values provided in the clinical database for each BL drawn:

In order to appropriately manage replicate values for analysis purposes, the individual GM of all values will be computed for each BL after managing extreme values as described:

- If a value is < LLOQ, then use the computed value LLOQ/2
- If a value is between  $\geq$  LLOQ and  $\leq$  ULOQ, then use the value
- If a value is  $\geq$  ULOQ, then use the computed value ULOQ

## 4.4.2.2 Seroprotection

Not applicable

#### **4.4.2.3** Fold-rise

The derived endpoint fold-rise is driven by both baseline and post-baseline computed values and will be computed using the FDA definition as follows. Generally, for extreme values, this algorithm minimizes the numerator and maximizes the denominator.

- If the baseline computed value is < LLOQ and the post-baseline computed value is < LLOQ then the fold-rise is 1
- If the baseline computed value is  $\geq$  LLOQ and the post-baseline computed value is  $\geq$  LLOQ then the fold-rise is post-baseline computed value / baseline computed value
- If the baseline computed value is ≥ LLOQ and the post-baseline computed value is < LLOQ then the fold-rise is (LLOQ/2)/baseline computed value
- If the baseline computed value is < LLOQ and the post-baseline computed value is ≥ LLOQ then the fold-rise is post-baseline computed value / LLOQ

If the computed value is  $\geq$  4-fold rise, then the derived  $\geq$  4-fold rise indicator will be "Yes" for that test, otherwise  $\geq$  4-fold rise will be "No".

Note: If baseline or post-baseline is missing, then fold-rise is missing.

#### 4.4.2.4 Seroconversion

Not applicable

#### 4.4.2.5 Seroresponse

hSBA vaccine seroresponse (definition proposed by the Center for Biologics Evaluation and Research [CBER] in 2016) for serogroups A, C, Y, and W is defined as:

- For a subject with a pre-vaccination titer < 1.8, the post-vaccination titer must be  $\ge 1.16$ .
- For a subject with a pre-vaccination titer ≥ 1:8, the post-vaccination titer must be at least 4-fold greater than the pre-vaccination titer.

hSBA vaccine seroresponse (definition used in study MET54) for serogroups A, C, Y, and W is defined as:

- For a subject with a pre-vaccination titer < 1:8, the post-vaccination titer must be  $\ge 1:8$ .
- For a subject with a pre-vaccination titer ≥ 1:8, the post-vaccination titer must be at least 4-fold greater than the pre-vaccination titer.

rSBA vaccine seroresponse is defined as:

- a post-vaccination rSBA titer ≥ 1:32 for subjects with pre-vaccination rSBA titer < 1:8,

   or
- a post-vaccination titer ≥ 4 times the pre-vaccination titer for subjects with pre-vaccination rSBA titer > 1:8.

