In general, categorical variables will be summarized and presented by frequency counts, proportion percentages, and confidence intervals (CIs). The 95% CIs of point estimates will be calculated using the normal approximation for quantitative data and the exact binomial distribution (Clopper-Pearson method) for percentages. For geometric mean titers (GMTs), 95% CIs of point estimates will be calculated using normal approximation assuming they are log-normally distributed.

Reverse cumulative distribution curve (RCDC) figures will be provided for the antibody titers against meningococcal serogroups and the antibody concentrations against tetanus toxoid contained in MenACYW conjugate vaccine.

In summary, descriptive analyses on A, C, Y, and W serogroups will include but not be limited to:

- hSBA and rSBA GMTs and 95% CI
- hSBA and rSBA titer distribution and RCDC
- Percentage of subjects with hSBA titer $\geq 1:4$ and $\geq 1:8$ and 95% CI
- Percentage of subjects with rSBA titer ≥ 1.8 and ≥ 1.128 and 95% CI

Percentage of subjects with hSBA and rSBA titer ≥4-fold rise from prevaccination to post-vaccination, and 95% CI

 Percentage of subjects with hSBA and rSBA vaccine seroresponse* rate and 95% CI

*hSBA vaccine seroresponse (definition proposed by the Center for Biologics Evaluation and Research [CBER] in 2016) for serogroups A, C, Y, and W is defined as:

- For a subject with a pre-vaccination titer < 1:8, the post-vaccination titer must be ≥ 1:16.
- For a subject with a pre-vaccination titer ≥ 1:8, the post-vaccination titer must be at least 4-fold greater than the pre-vaccination titer.

hSBA vaccine seroresponse (definition used in study MET54) for serogroups A, C, Y, and W is defined as:

- For a subject with a pre-vaccination titer < 1:8, the post-vaccination titer must be ≥ 1:8.
- For a subject with a pre-vaccination titer ≥ 1:8, the post-vaccination titer must be at least 4-fold greater than the pre-vaccination titer

rSBA vaccine seroresponse is defined as:

• a post-vaccination rSBA titer \geq 1:32 for subjects with pre-vaccination rSBA titer < 1:8,

or

• a post-vaccination titer ≥ 4 times the pre-vaccination titer for subjects with pre-vaccination rSBA titer ≥ 1:8.

In summary, descriptive analyses on anti-tetanus antibody concentrations will include but not be limited to:

- Geometric mean concentrations (GMCs) and 95% CI

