1.2 Background of the Investigational Product

1.2.1 Clinical

The MenACYW conjugate vaccine formulation was finalized based on data provided by 2 studies: MET28, a Phase I study in infants, toddlers, and adults 18 to 55 years of age; and MET32, a Phase I/II study in toddlers.

The formulation has been evaluated in over 1639 subjects (infants, toddlers, adolescents, and adults > 56 years of age) in completed studies MET39, MET44, MET50, and MET54. MenACYW conjugate vaccine is also being evaluated in ongoing Phase III studies (MET51 and MET57 in toddlers, MET35 in children (2 to 9 years of age), MET43 and MET56 in adolescents and adults, and MET49 in older adults ≥ 56 years of age). The relevant Phase II studies are discussed below.

MenACYW conjugate vaccine was found to be well tolerated and no unanticipated or new significant safety concerns have been identified in the clinical trials completed to date or in the ongoing MET56 study, where the MenACYW conjugate vaccine is administered to adolescents or adults who have received a dose of a meningococcal quadrivalent conjugate vaccine 4 to 10 years earlier.

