The frequency and percentage of subjects who had solicited injection site and systemic reactions and their 95% CIs will be provided. These events will be tabulated by type of reactions and intensity for each study group. These events will also be summarized by other categories specified in the endpoints (e.g., time of onset, number of days of occurrence, action taken).

Unsolicited AEs will be collected, coded, and summarized by MedDRA system organ class and PT. For each unsolicited AE, the number of subjects with at least one instance of that event will

hSBA vaccine seroresponse (definition used in study MET54) for serogroups A, C, Y, and W is defined as:

- For a subject with a pre-vaccination titer < 1.8, the post-vaccination titer must be ≥ 1.8 .
- For a subject with a pre-vaccination titer ≥ 1:8, the post-vaccination titer must be at least 4-fold greater than the pre-vaccination titer.

rSBA vaccine seroresponse is defined as:

• a post-vaccination rSBA titer ≥ 1.32 for subjects with pre-vaccination rSBA titer ≤ 1.8 ,

or

• a post-vaccination titer \geq 4 times the pre-vaccination titer for subjects with pre-vaccination rSBA titer \geq 1:8.

^a hSBA vaccine seroresponse (definition proposed by the Center for Biologics Evaluation and Research [CBER] in 2016) for serogroups A, C, Y, and W is defined as:

[•] For a subject with a pre-vaccination titer < 1.8, the post-vaccination titer must be ≥ 1.16 .

[•] For a subject with a pre-vaccination titer ≥ 1:8, the post-vaccination titer must be at least 4-fold greater than the pre-vaccination titer.

be reported. Unsolicited AEs will also be tabulated by intensity and relatedness of study vaccine and by other categories specified in the endpoints.

Immediate reactions, SAEs, and any event that leads to subject withdrawal from the study will be tabulated separately.

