## 4 Endpoints and Assessment Methods

## 4.1 Immunogenicity

See Section 9.1 of the protocol.

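### As printed, SAP 4.4.2.5 has no rSBA seroresponse rule for a baseline of exactly 1:8, which the protocol's rule covers; check the sign in the source SAP and in the program

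*SAP*

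**What the plan says.** SAP 4.4.2.5 (Seroresponse) gives rSBA seroresponse in two branches:

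- Lower branch: "a post-vaccination rSBA titer ≥ 1:32 for subjects with pre-vaccination rSBA titer < 1:8".
- Upper branch: "a post-vaccination titer ≥ 4 times the pre-vaccination titer for subjects with pre-vaccination rSBA titer > 1:8".

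The protocol's upper branch differs by one sign. The synopsis (Statistical Methods) has "a post-vaccination titer ≥ 4 times the pre-vaccination titer for subjects with pre-vaccination rSBA titer ≥ 1:8", and the footnote to Protocol 12.1.1.2 also includes 1:8 in the upper branch. Both hSBA definitions in SAP 4.4.2.5 include 1:8 in their upper branch too.

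Three other places bear on the point:

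- SAP 5.7 lists the added analysis set for persistence (FASP) as the change from the protocol and says nothing of seroresponse.
- Protocol 12.1 says that the SAP is to follow the protocol.
- For endpoint definitions SAP 4.1 says only "See Section 9.1 of the protocol". Protocol 9.1.1 lists titers and concentrations and contains no seroresponse rule, so that reference does not fill the gap. Section 4.4.2.5 is the SAP's only derivation of this endpoint.

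**The concern.** A response rule should assign every child with two valid titers to exactly one outcome. With one branch strictly below 1:8 and the other strictly above, the value 1:8 belongs to neither. That value is not remote: it is the boundary in every seroresponse definition here, and SAP 5.1.1.2.1 reports the share of children at or above it for rSBA.

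If the sign is in the source and is coded literally, the outcome for such a child depends on the program's default, either non-responder or missing. The rSBA seroresponse table could then contradict the table of 4-fold rises for the same children in any of the four serogroups, and the seroresponse denominator could shrink without explanation.

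**Working it through.** The plan states no figure to reproduce here, so the check is of the rule itself.

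**Inputs.** The two SAP branches (SAP 4.4.2.5), the protocol rule (synopsis and Protocol 12.1.1.2), the fold-rise rule (SAP 4.4.2.3), and MET54 denominators of 91 and 86 (Protocol 1.2.1.2). Group sizes for MET62 and the rSBA LLOQ are not given. The first is assumed near MET54; the second is varied.

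**Step 1: what the protocol requires at 1:8.** The upper branch asks for 4 × 8 = 32, that is 1:32. This equals the lower branch's cut-off, so the intended threshold at 1:8 is not in doubt.

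**Step 2: all pairs on a doubling scale.** Take baseline and post-vaccination titers from 2 to 8192: 13 × 13 = 169 pairs.

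| Rule | Pairs with no rule | Of these, responders under the protocol |
|---|---|---|
| Protocol synopsis | 0 | – |
| SAP as printed | 13 (all with baseline 8) | 9 (post-vaccination 32 to 8192) |

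At every other baseline the SAP and the protocol agree.

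**Step 3: agreement with the 4-fold indicator.** Suppose LLOQ ≤ 8 and baseline b ≥ 8. If the post-vaccination titer p is at or above the LLOQ, SAP 4.4.2.3 applies: "then the fold-rise is post-baseline computed value / baseline computed value". Then p/b ≥ 4 is the same condition as p ≥ 4b. If p is below the LLOQ, the fold-rise is (LLOQ/2)/b ≤ 4/8 = 0.5, and the child is a non-responder under both rules. So the protocol's seroresponse and the 4-fold indicator must agree for every child with b ≥ 8. On the 11 × 13 = 143 grid pairs with b ≥ 8, and LLOQ set to 2, 4 or 8, the protocol rule gives 0 mismatches and the printed SAP rule gives 9. For example, 8 to 32 has fold-rise 32/8 = 4, yet has no seroresponse rule in the SAP.

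**Step 4: limit of that check.** If the LLOQ were 16, a baseline below it would be set to 16/2 = 8. A rise to 32 then has fold-rise 32/16 = 2 (no), while the protocol rule applied to computed values gives 32 ≥ 4 × 8 (yes). A correct program would fail the comparison, so it is valid only for LLOQ ≤ 1:8.

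**Step 5: size per affected child**, for a child who should be a responder:

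- Coded as a non-responder: the rate falls by 100/n, which is 100/91 = 1.10 or 100/86 = 1.16 points.
- Left out of the denominator: the rate falls by 100 × (1 − r)/(n − 1), where r is the true rate. This is 0 at r = 100%. At r = 90% it is 10/90 = 0.11 points (n = 91) or 10/85 = 0.12 points (n = 86).

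The share of children at 1:8 is not in the documents. Purely as illustration, take 188 children who all respond under the protocol, with 2%, 5% or 10% at 1:8 (4, 9 or 19 children) coded as non-responders. The reported rate would be 97.9%, 95.2% or 89.9% instead of 100%. The share could equally be zero.

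**The case against.** The strongest objection is that the sign may not be in the SAP at all. In the text as read from the PDF, other comparison signs look wrong. Protocol 1.2.1 has "adolescents, and adults > 56 years of age" and, later in the same section, the same age limit with ≥. The Grade 2 upper bound for erythema and swelling in SAP 4.4.1.1.1 is ≤ 50 mm, against < 50 mm in Protocol Table 9.1. In SAP 4.4.2.5 some titers show a point for the colon. This stands as a reason for doubt, but it does not settle the matter: the disputed line renders its other ≥ sign and its colon correctly. An artefact is possible, not shown.

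A second objection is that the intent can be recovered. The protocol, the hSBA rules beside it and the silence of SAP 5.7 all point to ≥ 1:8, and harm requires a programmer to follow one odd sign against all of them. That is fair and limits the severity. It does not remove the need to correct an operative definition if the source carries the error.

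A reader might go further and infer that the rule exists in three competing forms, because the lower branch in the Protocol 12.1.1.2 footnote reads "for subjects with pre-vaccination rSBA titer ≤ 1.8". The documents do not support that. The sign there is probably a misread, and it would change no classification: at 1:8 both branches ask for 1:32, and the two protocol texts agree on all 169 pairs.

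**Conclusion.** The point holds as a conditional, minor correction. As printed, the SAP leaves a baseline rSBA titer of exactly 1:8 without a rule, and this departs from the protocol without being declared. Whether it is a real error depends on the source SAP printing the strict sign; whether results change depends on the program following it.

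The total effect cannot be estimated, because the number of children at 1:8 is unknown and may be zero. Per responder wrongly coded as a non-responder, a group rate falls by about 1.1 to 1.2 points, on the assumption of groups of 91 and 86. The study is descriptive throughout (Protocol 12.1.1.1, SAP 5.1.1.1), so no test or success criterion is affected. A reader might infer that the SAP deliberately redefined seroresponse, or that reported rates are already wrong. Nothing in the documents supports the first, and no program or result is available to show the second.

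**What to change.** Look at the sign in the source SAP. If it is the strict one, change the upper rSBA branch in SAP 4.4.2.5 to ≥ 1:8 to match the protocol. Every baseline then falls in exactly one branch. In either case, confirm that the program counts a child with baseline 1:8 as a responder at a post-vaccination titer of 1:32 or above.

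If the rSBA LLOQ is at or below 1:8, add one program check: for every child with baseline ≥ 1:8 and both titers available, rSBA seroresponse must equal the 4-fold indicator. Do not use this check with a higher LLOQ.

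The cost is one look at a file, at most one character, and one check. No new data or analysis is needed.
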